3.2. Inclusion Criteria

Potential subjects must satisfy all the following criteria to be enrolled in the study:

Inclusion Criteria after Screening:

The subject must:

- 1. Read, understand, and sign the STATEMENT OF INFORMED CONSENT and receive a fully executed copy of the form.
- 2. Appear able and willing to adhere to the instructions set forth in this clinical protocol.
- 3. Be at least 40 years of age and not greater than 70 years of age at the time of consent.
- 4. Own a wearable pair of spectacles if required for their distance vision.
- 5. Be an adapted soft contact lens wearer in both eyes (i.e. worn lenses a minimum of 2 days per week for at least 6 hours per wear day, for 1 month or more duration).
- 6. Either already be wearing a presbyopic contact lens correction (e.g., reading spectacles over contact lenses, multifocal or monovision contact lenses, etc.) or if not respond positively to at least one symptom on the "Presbyopic Symptoms Questionnaire" (Appendix D).

Inclusion Criteria at Baseline:

- 7. The subject's distance spherical equivalent refraction (vertex corrected if \geq -4.25 D) must be in the range of -1.25 D to -5.75 D or +0.75 D to +3.25 D in each eye.
- 8. The subject's refractive cylinder must be ≤ 0.75 D in each eye.
- 9. The subject's ADD power must be in the range of +0.75 D to +2.50 D.
- 10. The subject must have distance best corrected visual acuity of 20/20⁻³ or better in each eye.

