3.3. Exclusion Criteria

Potential subjects who meet any of the following criteria will be excluded from participating in the study:

Exclusion Criteria after Screening:

The subject must not:

- 1. Be currently pregnant or lactating.
- 2. Have any active or ongoing ocular or systemic allergies that may interfere with contact lens wear.
- 3. Have any active or ongoing systemic disease, autoimmune disease, or use of medication, which may interfere with contact lens wear. This may include, but not be limited to, diabetes, hyperthyroidism, Sjögren's syndrome, xerophthalmia, acne rosacea, Stevens-Johnson syndrome, and immunosuppressive diseases or any infectious diseases (e.g. hepatitis, tuberculosis).
- 4. Have any previous, or planned, ocular or intraocular surgery (e.g. radial keratotomy, PRK, LASIK, lid procedures, dacryocystorhinostomy, peripheral iridotomy/iridectomy, cataract surgery, retinal surgery, etc.).
- 5. Have a history of amblyopia, strabismus or binocular vision abnormality.
- 6. Use of any of the following medications within 1 week prior to enrollment: oral retinoid, oral tetracyclines, anticholinergics, oral phenothiazines, oral/inhaled corticosteroids. See section 9.1 for further examples.
- 7. Use of any ocular medication, with the exception of rewetting drops.
- 8. Have a history of herpetic keratitis.
- 9. Have a history of irregular cornea.
- 10. Have a history of pathological dry eye.
- 11. Have Participated in any contact lens or lens care product clinical trial within 30 days prior to study enrollment.
- 12. Be and employee or immediate family member of an employee of clinical site (e.g., Investigator, Coordinator, Technician).
- 13. Have any known hypersensitivity or allergic reaction to non-preserved rewetting drop solutions or sodium fluorescein.

Exclusion Criteria at Baseline:

The subject must not:

- 14. Have clinically significant (Grade 2 or greater) corneal edema, corneal vascularization, corneal staining, tarsal abnormalities or bulbar injection, or any other corneal or ocular abnormalities which would contraindicate contact lens wear.
- 15. Have any current ocular infection or inflammation.
- 16. Have any current ocular abnormality that may interfere with contact lens wear.

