5. TEST ARTICLE ALLOCATION AND MASKING

5.1. Test Article Allocation

The study lenses will be worn in a bilateral and random fashion using a 2x3 crossover design. A computer-generated randomization scheme will be used to randomly assign subjects, in blocks of 2, to one of the two lens wear sequences: Test/DT1MF/DT1MF or DT1MF/Test/Test. The randomization scheme will be stratified by site. The random scheme will be generated using the PROC PLAN procedure from Statistical Analysis System (SAS) Software Version 9.4 or higher (SAS Institute, Cary, NC).¹⁵

The study site must follow the randomization scheme provided and complete enrollment per the randomization list and not pre-select or assign subjects. Randomization will be performed at visit first visit prior to the first fitting. The following must have occurred prior to randomization:

- Informed consent must have been obtained.
- The subject must have met all eligibility criteria.
- The subject's screening and baseline information must have been collected.

When dispensing test articles, the following steps should be followed to maintain randomization codes:

- 1. Investigator or designee (documented on the Delegation Log) will consult the lens fitting schedule to obtain the test article assignment for that subject prior to dispensing.
- 2. Investigator or designee will record the subject's number on the appropriate line of the lens fitting schedule.
- 3. Investigator or designee will pull the appropriate test articles from the study supply. All test articles that are opened, whether dispensed (placed/fit on eye or dispensed outside the clinical site) or not, must be recorded on the Test Article Accountability Log in the "Dispensed" section.

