7.2. Detailed Study Procedures

VISIT 1

Subjects must report to the visit wearing their habitual contact lenses to accurately assess baseline PRO (MRD) performance. If the subject is not wearing their lenses they must be rescheduled.

	Visit 1: Screening				
Step	Procedure	Details			
1.1	Statement of Informed Consent	Each subject must read, understand, and sign the Statement of Informed Consent before being enrolled into the study. The Principal Investigator or his/her designee conducting the informed consent discussion must also sign the consent form. NOTE: The subject must be provided a signed copy of this document.			
1.2	Demographics	Record the subject's age, gender, race and ethnicity.			
1.3	Medical History and Concomitant Medications	Questions regarding the subject's medical history and concomitant medications.			
1.4	Habitual Lenses	Questions regarding the subject's habitual lens type and parameters.			
1.5	Habitual Lens Duration of Wear/Days per week	Questions regarding the subject's duration of contact lens wear and the minimum number of days they wear their lenses per week.			
1.6	Contact Lens History	Record the subject's correction type (i.e. monovision, multifocal, sphere with readers, etc.).			
1.7	Wear time and Comfortable Wear time with Habitual lenses	Record the subject's wear time and comfortable wear time with their habitual contact lenses.			
1.8	Eligibility after Screening	All responses to Screening Inclusion Criteria questions must be answered "yes" and all responses to Exclusion Criteria must be answered "no" for the subject to be considered eligible. If subject is deemed to be ineligible after screening, proceed to Final Evaluation and complete Subject Disposition. Refraction and Biomicroscopy forms are not required.			

	Visit 1: Baseline					
Step	Procedure	Details				
1.9	Baseline PRO (MRD) Questionnaires	The subject will evaluate the vision characteristics, comfort characteristics, and visual symptoms of their habitual lenses using the PRO (MRD) questionnaires.				
1.10	Ocular Symptoms	The subject will respond to a verbal openended symptoms questionnaire.				
1.11	Entrance Visual Acuity	Distance and near Snellen visual acuity will be measured for each eye with the subject's habitual contact lenses in place. For near measures use the ETDRS 2000 Series Chart 1 or 2. The acuity will be recorded to the nearest letter OD, OS and OU.				

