1.12	Lens Removal	Have the subject remove their habitual lenses and store in an approved storage solution.				
1.13	Subjective Refraction and Distance Visual Acuity	An optimal, binocular balanced distance sphero-cylindrical refraction will be performed. Record the refraction and distance visual acuity to the nearest letter. NOTE: Best distance visual acuity with sphero-cylindrical refraction must be at least 20/20 ⁻³ in each eye for the subject to be eligible in the study.				
1.14	Near ADD Determination	The near reading addition will be determined using the binocular crossed cylinder technique (BCC) at 40 cm.				
1.15	Ocular Dominance	Determine the distance ocular dominance with the best distance correction in place using a +1.00-blur test. If the results are equivocal use the sighting dominance test to determine the dominant eye used for the study.	Appendix E			
1.16	ADD Refinement	Place the BCC result in the trial frame and refine the near prescription with trial lenses (or flippers) under binocular conditions.				
1.17	Near Visual Acuity	Using the ETDRS 2000 Series Chart 1 or 2 near card placed at 40 cm. Record the near visual acuity OD, OS and OU at 40 cm.				

	Visit 1: Baseline		
Step	Procedure	Details	
1.18	Biomicroscopy	FDA Slit Lamp Classification Scale will be used to grade the findings and determine eligibility.	
		If any of these slit lamp findings are Grade 2 or higher, the subject will be discontinued. If discontinued a final examination must be completed.	
		If the clearance of the fluorescein needs to be expedited, preservative-free rewetting drops may be instilled.	
1.19	Eligibility after Baseline	All responses to Inclusion Criteria questions must be answered "yes" and all responses to Exclusion Criteria questions must be answered "no" for the subject to be considered eligible. If so, proceed to lens fitting.	
		If subject is deemed to be ineligible after baseline, proceed to Final Evaluation and complete all forms.	
		Visit 1: Treatment 1 Lens Fitting	
Step	Procedure	Details	
1.20	Randomization	Record the randomization ID.	
1.21	Lens Selection	Select the lens pair and power based on the randomization scheme, spherical equivalent refraction and fitting guide for each eye. Record the Test lens parameters (power and lot number).	Appendix F or G (Fitting Guide)

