13. ADVERSE EVENTS

13.1. Definitions and Classifications

Adverse Event (AE) – An AE is "any untoward medical occurrence, unintended disease or injury, or untoward clinical signs (including abnormal laboratory findings) in subjects, users or other persons, whether or not related to the investigational medical device."

Note: This definition includes events related to the investigational medical device or the comparator, and to the procedures involved. For users or other persons, this definition is restricted to events related to investigational medical devices.

An AE includes any condition (including a pre-existing condition) that:

- 1. Was not present prior to the study, but appeared or reappeared following initiation of the study.
- 2. Was present prior to the study but worsened during the study. This would include any condition resulting from concomitant illnesses, reactions to concomitant medications, or progression of disease states.

Note: Pregnancy must be documented as an adverse event and must be reported to the clinical monitor and to the Sponsor immediately upon learning of the event.

Serious Adverse Event (SAE) – An SAE is any adverse event that led to any of the following:

- Death
- Serious deterioration in the health of the subject that resulted in any of the following:
- Life-threatening illness or injury
- Permanent or persistent impairment of a body structure or a body function
- Hospitalization or prolongation of patient hospitalization
- Medical or surgical intervention to prevent life-threatening illness or injury or permanent impairment to a body structure or a body function.

- Chronic disease
- Foetal distress, foetal death or a congenital physical or mental impairment of birth defect.

Diagnoses and conditions that are considered Ocular Serious Adverse Events include, but not limited to:

- Microbial Keratitis (MK)
- Iritis (including cells in the anterior chamber)
- Permanent decrease in best spectacle corrected visual acuity equivalent to 2 acuity lines or greater
- Central Corneal Opacity
- Central Corneal Neovascularization
- Uveitis
- Endophthalmitis
- Hypopyon
- Hyphemia
- Penetration of Bowman's Membrane
- Persistent Epithelial Defect
- Limbal cell Damage leading to Conjunctivalization

Significant Adverse Events – are defined as events that are symptomatic and warrant discontinuation (temporary or permanent) of the contact lens wear

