NOTE: Hereafter, DAILIES TOTAL1* spherical lenses and DAILIES TOTAL1* Multifocal contact lenses will simply be referred to as delefilcon A contact lenses unless product distinction is necessary.

When hydrated and placed on the cornea, deletiicon A contact lenses act as a refracting medium to focus light rays on the retina.

INDICATIONS (USES)

DAILIES TOTAL1* (delefilion A) spherical soft contact lenses are indicated for the optical correction of refractive ametropia (myopia. and hyperopia) in phakic or aphakic persons with non-diseased eves with up to approximately 1,50 diopters (D) of astigmatism that does not interfere with visual acuity.

DAILIES TOTAL1* Multifocal (deleflicon A) soft contact lenses are indicated for the optical correction of refractive ametropia (myopia. and hyperopia) and/or presbyopia in phakic or aphakic persons with non-diseased eyes who may require a reading addition of +3.00 (D) or less and who may have up to approximately 1.50 diopters (D) of astigmatism that does not interfere with visual

The lenses are to be prescribed for single use, daily disposable wear. The lenses are not intended to be cleaned or disinfected and should be discarded after a single use.

CONTRAIND(CRTKOMB)(REAS(INS NOT TO USE) DO NOT use deleflicon A contact lenses when any of the following exists:

. Inflammation or infection of the anterior chamber of the eye

- Active disease, injury or abnormality affecting the cornea, conjunctiva, or eyelids
- Microbial Infection of the eye
- insufficiency of lacrimal secretion (dry eye) that interferes with contact lens wear
- Corneal hypoesthesia (reduced corneal sensitivity)
- Use of any medication that is contraindicated or interferes with contact lens wear, including eye medications
- Any systemic disease which may be exacerbated by or Interferes with contact lens wear
- · Allergic reactions or ocular irritation of the ocular surfaces or adnexa that may be caused by or exaggerated by the wearing of contact lenses
- Patient history of recurring eye or eyelid infections, adverse effects associated with contact lens wear, intolerance or abnormal ocular response to contact lens wear
- If eyes become red or irritated

WARNINGS

Advise patients of the following warnings pertaining to contact lens wear:

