DAILIES TOTAL1® Multifocal (delefilcon A) soft contact lenses Database Total: Immittoda (uderticon y soit contact reisea are indicated for the optical correction of refractive ametropia (myopia and hyperopia) and/or presbyopia in phakic or aphakic persons with non-diseased eyes who may require a reading addition of +3.00 (D) or less and who may have up to approximately 1.50 diopters (D) of astigmatism that does not interfere with visual acuity.

The lenses are to be prescribed for single use, daily disposable wear. The lenses are not intended to be cleaned or disinfected and should be discarded after a single use.

CONTRAINDICATIONS (Reasons Not To Use) DO NOT use delefilcon A contact lenses when any of the following exists:

 Inflammation or infection of the anterior chamber of the eye
 Active disease, injury or abnormality affecting the cornea, conjunctiva, or evelids

CR-6479, v 3.0

- Microbial infection of the eye
 Insufficiency of lacrimal secretion (dry eye) that interferes with contact lens wear
 Corneal hypoesthesia (reduced corneal sensitivity)
- Use of any medication that is contraindicated or interferes
- with contact lens wear, including eve medications Any systemic disease which may be exacerbated by or
- interferes with contact lens wear Allergic reactions or ocular irritation of the ocular surfaces or adnexa that may be caused by or exaggerated by the wearing of contact lenses
- Detains history of recurring eye or eyelid infections, adverse effects associated with contact lens wear, intolerance or abnormal ocular response to contact lens wear
- · If eves become red or irritated

WARNINGS

Advise patients of the following warnings pertaining to contact lens wear:

Problems with contact lenses and lens care products could

- result in serious injury to the eye. It is essential that patients follow their eye care professional's directions and all labeling instructions for proper use of lenses and lens care products.

 Serious eye problems, including corneal ulcers, can
- develop rapidly and lead to loss of vision.

 Daily wear lenses are not indicated for overnight wear, and patients should be instructed not to wear lenses while sleeping. Clinical study results have shown that the risk of serious adverse reactions is increased when contact lenses
- Studies² have shown that contact lens wearers who are smokers have a higher incidence of adverse reactions than ionsmokers.

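### Apart from past herpetic keratitis, no listed exclusion covers the control label's contraindication for a history of recurring infection or lens-related problems (minor subject-protection gap)

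*Combined protocol and SAP*

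**What the plan says.** The protocol reproduces two inserts for the control lens, one in Appendix C (March 2016) and one inside the Appendix G fitting guide (December 2019). Each lists a patient history among the reasons not to use the lens. Appendix C gives it as "Patient history of recurring eye or eyelid infections, adverse effects associated with contact lens wear, intolerance or abnormal ocular response to contact lens wear", and Appendix G repeats it ("history of recurring eye or eyelid infections, adverse effects associated with contact lens wear").

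Section 5.1 randomizes each subject "to one of the two lens wear sequences: Test/DT1MF/DT1MF or DT1MF/Test/Test", so everyone who completes the study wears the control lens.

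Section 3.3 and the synopsis carry the same 16 exclusions. On infection they name a history of herpetic keratitis (8) and, at baseline, "Have any current ocular infection or inflammation" (15). Exclusions 14 and 16 concern graded slit-lamp findings and ocular abnormalities at baseline. At step 1.8, "all responses to Exclusion Criteria must be answered 'no' for the subject to be considered eligible"; step 1.19 applies the same rule after baseline. Section 4.1 then randomizes a subject who meets all the criteria.

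On the inclusion side, item 5 in section 3.2 requires the subject to "Be an adapted soft contact lens wearer in both eyes", with a minimum of 2 days a week, 6 hours per wear day, for 1 month.

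**The concern.** Most of the control label's contraindications have a counterpart among the exclusions: active infection or inflammation, ocular surface abnormality, dry eye, interfering medication, systemic disease and allergy. The history item has no general counterpart, and no reason for leaving it out is given. A site that follows the listed criteria exactly can therefore admit someone whom the control label says not to fit, and whether anyone acts on that history depends on the site.

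There is also an asymmetry. Section 8.2 withdraws a subject who has a corneal infiltrative event during the study, but no entry criterion asks about earlier ones. What is at stake is the protection of a small, uncounted group of subjects, not the comparison of lenses.

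**Working it through.** The plan states no figure on this point, so the main check sets the label item beside the entry rules.

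**Step 1. Coverage of the four parts of the label item**

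| Part of the label history | Reached by a listed criterion | Left uncovered |
|---|---|---|
| Recurring eye or eyelid infection | 8 (herpetic keratitis); 15 if active at baseline | Other recurrent infection that is quiet at baseline |
| Adverse effects of lens wear | 14–16, only if signs are still present | Resolved events |
| Intolerance | No exclusion; inclusion 5 makes current intolerance unlikely | Past intolerance in a now-adapted wearer |
| Abnormal ocular response | 14 and 16, only if still visible | Resolved responses |

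The other ocular-history exclusions (4 surgery, 5 amblyopia, strabismus or binocular abnormality, 9 irregular cornea, 10 pathological dry eye) do not reach these gaps. Exclusion 13 concerns rewetting drops and fluorescein, not reactions to lenses.

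**Step 2. Whether another step closes the gap before a lens goes on.** Step 1.3 takes medical history. Steps 1.4 to 1.6 record habitual lens type, duration and days of wear, and correction type. No visible step asks about past lens-related events or ties the answer to eligibility. Step 1.21 invokes the fitting guide after randomization, for choosing the lenses: "Select the lens pair and power based on the randomization scheme, spherical equivalent refraction and fitting guide for each eye". The dispensing criteria at step 1.30 concern acuity, vision, comfort and fit, not history. An adapted wearer with quiet eyes and, say, a past contact-lens peripheral ulcer can pass every listed item.

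**Step 3. Planned exposure (intervals from Table 3)**

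- Total wear: 3 + 7 + 3 + 7 + 7 = 27 days.
- DT1MF/Test/Test: control wear (3 ± 1) + (7 ± 1) = 10 days, range 8–12; 10/27 = 37%.
- Test/DT1MF/DT1MF: control wear (3 ± 1) + (7 ± 1) + (7 ± 1) = 17 days, range 14–20; 17/27 = 63%.
- Longest planned gap between slit-lamp examinations: 7 + 1 = 8 days.

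**Step 4. Change in wear for an occasional wearer.** At the inclusion 5 minimum, weekly wear is 2 × 6 = 12 hours. Section 4.1 advises at least 6 hours every day, or 7 × 6 = 42 hours. That is 42/12 = 3.5 times the minimum habitual wear, whichever study lens is on the eye.

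**Step 5. Frequency.** The documents give no prevalence of such a history. The enrolment target of 130 is the whole sample, with allowance for screen failures and dropout, so it does not estimate how many subjects are affected.

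**The case against.** The case for leaving the criteria alone has four parts.

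First, the label item is not wholly ignored. Exclusion 8 covers one infection history, and exclusions 14 to 16 remove anyone whose infection, inflammation or abnormal response is still present. This stands: a reader might infer that nothing in the list touches the contraindication, and the documents do not support that. The gap is resolved history other than herpetic keratitis.

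Second, subjects already wear soft lenses, and most of the label item concerns lens wear in general rather than this material, so the control lens replaces wear that is already happening. This stands in part. The documents show no added risk for a daily wearer, but the argument is weaker for someone who comes in at 2 days a week and is moved to every day.

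Third, the investigator has the label and can act on it. Section 1.4 calls for normal clinical guidelines and points to the insert. The fitting guide asks for a thorough case history and counts other contraindications against a candidate. Slit-lamp examination takes place at every visit, and section 8.2 allows withdrawal on safety judgment. These safeguards narrow the exposure, but none is an entry rule for this history, and the section 8.2 clause works only after entry.

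Fourth, copying the label line unchanged could exclude adapted wearers for trivial past events, so a sponsor may have had reason not to copy it. That also stands, and is why the change below is graded. Where to cut for past intolerance or abnormal response is largely a matter of preference, and inclusion 5 already addresses part of it.

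**Conclusion.** The point holds as a minor subject-protection gap. By the listed rules, an adapted wearer with quiet eyes and a history of recurring infection (other than herpetic keratitis) or of a past lens-related adverse event is eligible. Such a subject is then planned to wear the control lens for 10 days (8–12) or 17 days (14–20) of 27. How often this would happen cannot be estimated from the documents.

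A reader might go further and infer that subjects are placed at demonstrably higher risk, or that the results are compromised. The documents support neither inference: they show no excess risk over habitual wear for this group, and nothing here bears on the endpoints, power or conclusions.

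The conclusion assumes that eligibility is decided as steps 1.8 and 1.19 describe. The content of Appendix F, the Investigator's Brochure and the eCRF history questions cannot be seen. If any of them asks about this history and ties the answer to entry, the gap is smaller or absent. Confidence is therefore medium.

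**What to change.** Add one screening exclusion to section 3.3 and the synopsis, applied at step 1.8 and asked with the history at steps 1.3 to 1.6. Suggested text: *a history of recurrent infection of the eye or eyelid, or of a serious or significant contact-lens-related ocular adverse event as defined in section 13.1*.

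Section 13.1 already supplies the threshold, since significant events "are defined as events that are symptomatic and warrant discontinuation (temporary or permanent) of the contact lens wear". The lens-related qualifier is needed because the significant list also includes corneal events unrelated to lens wear. Milder past events, and past intolerance or abnormal response in a wearer who is now adapted, should be left to the investigator's judgment against the insert. The protocol should say that the criterion applies the label item at a graded threshold and does not reproduce it in full.

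The cost is one eligibility line and one screening question in an amendment. The sample size calculation does not change. The downsides are a slightly smaller eligible pool, by an amount the documents do not allow one to estimate, and only partial conformity with the label.
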